### Extended Statistical Analysis Plan

Baseline characteristics between participants enrolled in the study and those screened but not enrolled, and between those enrolled during the control period and those enrolled during the intervention period, will be compared using chi-square tests and t-tests.

**Reach** is defined as the proportion of the target population who participate in the intervention. We will assess reach by calculating the percentage of patients and caregivers who received the pamphlet and video decision aids out of the total number of patients and caregivers enrolled in the intervention period.

**Effectiveness** of the intervention will be assessed through the primary outcome of decision quality: the extent to which medical decision making reflects the considered preferences of a well-informed patient. As such, co-primary endpoints were chosen comprising the two main International Patient Decision Aid Standards domains of decision quality—knowledge and values-choice concordance.

**Knowledge:** A 10-item knowledge test was developed by the study team and validated by clinicians and patients. Consistent with methods of Sepucha et al., the study team created a list of knowledge items based on clinical needs, local post-LVAD education standards, and needs assessment work with patients. We then surveyed patients, caregivers, MCS coordinators, and physicians to narrow the list and determine the key knowledge items and assure content validity. The acceptability of this measure was further assessed with patients and caregivers in a pilot of the trial protocol. Improvement in knowledge from baseline 1 (enrollment) survey to baseline 2 (post-education) survey was a co-primary endpoint.

To assess the change in patient DT LVAD knowledge over time, we will fit a linear mixed model proposed for the analysis of stepped wedge designs. This model accounts for the repeated measures within subject, included a random effect for site and fixed effect indicators of intervention group and stepped wedge time period. This model adjusts for trends over time, assuming that changes occur similarly across all sites. We will assess any differences in baseline covariate distribution by intervention group, and will include covariates that are imbalanced by group in this linear mixed model. We will evaluate whether the change in knowledge score (percent correct) between baseline 1 and baseline 2 was different between the control and intervention groups.

**Values-Choice Concordance:** A values scale was also developed, modeled after a well-accepted values evaluation tool. During previous needs assessment work, one value rose above all others in considering DT LVAD: maximizing chances of survival with aggressive medical care versus not. We developed a single-item, 10-tier Likert values measure using the dichotomy of “Do everything I can to live longer, even if that means having major surgery and being dependent on a machine” (score 1) versus “Live with whatever time I have left, without going through major surgery or being dependent on a machine” (score 10). For caregivers, this read as “Do everything my loved one can to live longer, even if that means having major surgery and being dependent on a machine” (score 1) versus “Have my loved one live with whatever time he/she has left, without going through major surgery or being dependent on a machine” (score 10). At 1 month post-enrollment, we will create a dichotomous variable of whether the patient wanted to get the LVAD or did not want to get the LVAD (DT LVAD or medical management without LVAD), and patients and caregivers will report the patient’s treatment choice. Concordance between 1-month value score and patient/caregiver-reported treatment choice at 1-month is the other co-primary endpoint. Secondary outcome of concordance between 1-month value score and actual treatment received by 6-months will also be assessed. Actual treatment received by 6

months is recorded on the patient's medical record review and is defined as whether the patient had been implanted with the LVAD by 6 months or not implanted.

To assess values-choice concordance, we will calculate the Kendall's tau correlation coefficient between the stated values score at 1 month and each of the treatment outcomes (patient/caregiver-reported treatment choice at 1 month, actual treatment received at 6 months), and look at the difference in this correlation coefficient by intervention group. To generate a confidence interval for this difference, we will perform 500 bootstrap samples and calculate the 2.5 and 97.5th percentiles.

**Secondary outcomes** measures include the following for both patients and caregivers:

- **Acceptability:** We will measure acceptability of education materials by using a modified version of decision aid acceptability developed by Barry et al.
- **Decision Conflict:** We will use the validated 15-item decision conflict measure developed by O'Connor et al.
- **Decision Regret:** We will use the validated 5-item decision regret scale.
- **Patient Health Questionnaire-2:** To assess depression in patients and caregivers at baseline and after their decision.
- **Perceived Stress Scale:** To assess the stress patients and caregivers feel during the decision making process.

And the following for patients only:

- **Control Preferences Scale (preferred and actual):** We will measure the participants' preferred role in decision making using the validated Control Preferences Scale and their actual control participation.
- **PEACE Illness Acceptance Measure:** For patients, we will assess patients' acceptance of their current heart failure illness and whether that impacts their decision to accept or decline DT LVAD.
- **Quality of Life (EQ Visual Analogue Scale):** For patients, we will assess their self-reported quality of life score through only the Visual Analogue Scale portion of the EQ5D, both pre and post decision.

And for caregivers only:

- **The Preparedness for Caregiving Scale:** For caregivers, we will assess their level of preparedness, both mentally and physically, pre and post decision.
- **Family Satisfaction with Care:** For caregivers, we will assess their satisfaction with the decision making process and their involvement.

Secondary outcomes data will be scored and summarized according to the methods previously validated and published for each measure. Significance for differences by intervention group at specified time points for the categorical outcome scales will be determined using Chi-square tests. Differences in the continuous outcome scales by intervention group will be assessed via the linear mixed model described previously.

Missing data will be characterized at each time point. Analysis will account for missing data and will relax the missing data assumptions to missing at random conditional on observed data.

**Adoption** is defined as the absolute number, proportion, and representativeness of settings who are willing to initiate a program. We will calculate the total number of programs in the study who used the intervention at their program.

**Implementation** is defined as the extent to which the intervention is implemented as intended. Decision aid use will be reported by the study team with a checklist for each patient enrolled. We will calculate the percentage of patients who received the pamphlet and the video decision aids in certain ways (e.g. percent who received the decision aids from clinical personnel, percent who viewed the video in a clinical setting).

**Maintenance** will be assessed primarily by calculating the total number sites that decide at the conclusion of the study to maintain, modify, or discontinue the use of the decision aids.

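### Reach is defined on the target population but calculated only among people already enrolled, so it cannot show how much of that population was reached

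*SAP*

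**What the plan says.** Four statements in the SAP bear on this point.

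- The Reach paragraph opens with the concept: reach "is defined as the proportion of the target population who participate in the intervention".
- The next sentence gives the calculation. The numerator is the "percentage of patients and caregivers who received the pamphlet and video decision aids", and the denominator is given by "out of the total number of patients and caregivers enrolled in the intervention period".
- The sentence just before that paragraph plans a comparison of "Baseline characteristics between participants enrolled in the study and those screened but not enrolled". The SAP therefore expects some screened people to remain outside the study, and expects to hold some data on them.
- The Implementation paragraph names the source of data on use of the aids: "Decision aid use will be reported by the study team with a checklist for each patient enrolled". It then plans a second set of delivery percentages: "We will calculate the percentage of patients who received the pamphlet and the video decision aids in certain ways".

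The SAP does not say what the target population is. It gives no expected or observed number screened, eligible, enrolled or receiving the aids.

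**The concern.** The definition and the formula stand in consecutive sentences and have different denominators. The definition looks outward to everyone the decision aids are meant for. The formula looks only at those who have already joined the study in its intervention period.

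A denominator of enrollees removes the step at which most people are likely to be missed, namely entry to the study. A site that enrols half of its eligible patients and one that enrols nearly all of them would report the same reach if both hand the aids to the same fraction of enrollees. A high delivery rate among consenting participants could then be published as population reach.

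Nothing else in the SAP fills the gap. The comparison of enrolled with non-enrolled people describes how they differ, but it gives no proportion reached. The Implementation percentages are themselves delivery figures, with data from enrolled patients. As calculated, reach is close to one of these, and no component of the evaluation reports how much of the patient population was covered.

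**Working it through.** The plan states no reach figure, so there is nothing to reproduce. The check compares the defined quantity with the calculated one.

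**Symbols** (the SAP gives a value for none of them)

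- *e*: enrolled share of eligible people in the intervention period
- *r*: proportion of enrollees who receive the aids
- *q*: proportion of eligible, non-enrolled people who receive the aids

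**Formulas**

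- Quantity the SAP calculates: *r*
- Quantity the SAP defines, taking the target population as all eligible people: *e·r* + (1 − *e*)·*q*
- Difference: *r* − [*e·r* + (1 − *e*)·*q*] = (1 − *e*)(*r* − *q*)

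The difference is zero only if *e* = 1 or *q* = *r*. It is an overstatement if *q* < *r* and an understatement if *q* > *r*. The calculated figure does not contain *e* at all. That needs no assumed number.

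**Illustration.** Assumed values: *e* = 50%, 70%, 90%; *r* = 70% and 95%; *q* = 0, *r*/2 and *r*. Entries are the overstatement in percentage points.

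| *r* | *q* | *e* = 50% | *e* = 70% | *e* = 90% |
|---|---|---|---|---|
| 70% | 0 | 35.0 | 21.0 | 7.0 |
| 70% | 35% | 17.5 | 10.5 | 3.5 |
| 70% | 70% | 0 | 0 | 0 |
| 95% | 0 | 47.5 | 28.5 | 9.5 |
| 95% | 47.5% | 23.75 | 14.25 | 4.75 |
| 95% | 95% | 0 | 0 | 0 |

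For example, with *r* = 95%, *q* = 0 and *e* = 50%: (1 − 0.50)(0.95 − 0) = 0.475.

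**Opposite sign.** With *e* = 50%, *r* = 70% and *q* = 80%: (1 − 0.50)(0.70 − 0.80) = −0.05, an understatement of 5 points.

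**Bounds on population reach at *r* = 95%.** The lower bound takes *q* = 0 and equals *e·r*. The upper bound takes *q* = 1 and equals *e·r* + (1 − *e*).

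| *e* | SAP figure | Lower bound | Upper bound |
|---|---|---|---|
| 50% | 95% | 47.5% | 97.5% |
| 70% | 95% | 66.5% | 96.5% |
| 90% | 95% | 85.5% | 95.5% |

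The SAP's figure is 95% in every row. At *r* = 70% the lower bounds are 35%, 49% and 63%, and the SAP's figure is 70% throughout.

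**The case against.** The best defence is that the SAP leaves the target population undefined and does not speak of eligibility. Both are commonly left to the protocol, which is not at hand. If the protocol took the target to be participants enrolled during a site's intervention period, the two sentences would agree. On this view the opening sentence is a general definition taken from the evaluation framework, the second is the trial's explicit measure, and a reader can see that it is receipt among enrollees. What remains is a matter of labelling.

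This does not remove the problem. Nothing in the SAP equates the target population with enrollees, and on that reading reach becomes a delivery measure hardly distinct from Implementation. The SAP would still need to say so, and relabelling does that.

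Three further objections have some force.

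- Screened people who did not enrol may include the ineligible, and the SAP does not show that eligibility is recorded. This stands, so the remedy needs a fallback.
- The sizes come wholly from assumed values, and even the sign is open. This also stands. The 47.5-point figure is the extreme of the assumed range, not an estimate for this trial.
- Dividing recorded receipt by all screened and eligible patients counts every non-enrolled patient as unreached, and so mixes refusal of research with failure to get the aids. This is true, and it is why that percentage can be offered only as a lower bound.

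**Conclusion.** The concern holds as a minor point. The SAP defines reach on the target population and fixes a formula that measures receipt among enrollees, with no correction elsewhere in the document. The conclusion that the figure is insensitive to the enrolled share follows from the formula alone.

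The size cannot be known from the SAP. Over the assumed range (receipt among enrollees 70% to 95%, receipt among the non-enrolled between zero and the enrollee rate), the overstatement is 0 to 47.5 points at 50% enrolment, 0 to 28.5 at 70% and 0 to 9.5 at 90%. It turns into an understatement if non-enrolled people receive the aids more often than enrollees. These sizes take the target population to be all eligible people, which the SAP does not state.

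No test, model or decision rule in the SAP uses the reach figure, and neither knowledge nor values-choice concordance is touched.

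**What to change.** State what the target population is, and rename the present percentage as receipt among enrolled participants. Beside it report two descriptive figures for patients in the intervention period:

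1. the enrolled share of those screened and eligible;
2. the number with recorded receipt divided by all screened and eligible patients, stated as a lower bound on reach because receipt is recorded only for enrolled patients.

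Caregivers should enter the wider denominator only if caregivers of non-enrolled patients were counted.

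The cost is a change of wording and two extra percentages, with no new model. The data needed are counts of screened and eligible patients at sites during their intervention period. If eligibility was not recorded for those who did not enrol, report the enrolled share of all those screened and say that this was done. The drawback of the second percentage should be stated with it: it understates reach wherever sites also gave the aids to patients outside the study.

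### The knowledge model has one random effect for site and a period trend assumed common to all sites, with nothing to relax or check this; if sites shift by period, its standard error would be too small.

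*SAP*

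**What the plan says.** The SAP is one section, Extended Statistical Analysis Plan. Under Effectiveness, the Knowledge paragraphs set the endpoint: "Improvement in knowledge from baseline 1 (enrollment) survey to baseline 2 (post-education) survey was a co-primary endpoint". For its analysis, "we will fit a linear mixed model proposed for the analysis of stepped wedge designs". That model accounts for repeated measures within subject and "included a random effect for site and fixed effect indicators of intervention group and stepped wedge time period". The next sentence states the assumption: "This model adjusts for trends over time, assuming that changes occur similarly across all sites". The question to be answered is "whether the change in knowledge score (percent correct) between baseline 1 and baseline 2 was different between the control and intervention groups".

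The same model serves beyond the co-primary. Under Secondary outcomes: "Differences in the continuous outcome scales by intervention group will be assessed via the linear mixed model described previously".

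The SAP does not let the period trend or the intervention effect vary by site. It names no robust or small-sample standard error, and it plans no sensitivity analysis or display that would test the assumption.

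**The concern.** In a stepped wedge, intervention status is set by site and period. A shift shared by all patients in one site during one period therefore sits at the level at which the effect is estimated. One constant per site cannot absorb it. The model then treats patients in the same site and period as independent once the site constant and the common period effect are removed, and it understates the standard error.

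The assumption deserves a check here because the outcome is the gain in knowledge from enrolment to after education. That gain depends on how each programme teaches, and teaching can change at one programme without changing elsewhere. If it does, the interval for the knowledge co-primary would be too narrow and its test would reject too often. The continuous secondary scales inherit the same structure. The education mechanism is most direct for knowledge and less so for scales such as perceived stress or the EQ visual analogue scale.

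**Working it through.** **No figure to reproduce.** The SAP states no site count, sample size, SD, intraclass correlation or power. Every input below is an assumption.

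**Inputs.** 360 patients in two layouts:
- 6 sites × 4 periods (3 steps) × 15 per site-period = 360
- 12 sites × 5 periods (4 steps) × 6 per site-period = 360

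Individual SD of the change score σ = 15 points, site SD 3 points, no true effect, nominal two-sided 5%. The site-by-period SD τ runs from 0 to 5 points. The change score is taken as the outcome, with the site and period terms acting on it. This reading favours the plan: when the two scores were modelled with group-by-visit as the only change term, interval coverage was lower.

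**Step 1: approximation by hand.** With m patients per site-period:
- ρ = τ² / (τ² + σ²)
- variance inflation D = 1 + (m − 1)ρ
- true over reported standard error ≈ √D
- type I error ≈ 2 × [1 − Φ(1.96/√D)]

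For τ = 5 and m = 15: ρ = 25/250 = 0.10, D = 1 + 14 × 0.10 = 2.4, √D = 1.55, and 1.96/1.55 = 1.27, so the error is about 21%. For τ = 1 and m = 15: ρ = 1/226 = 0.0044, D = 1.06, √D = 1.03, error about 5.7%. For τ = 5 and m = 6: D = 1 + 5 × 0.10 = 1.5, √D = 1.22, error about 11%.

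**Step 2: simulation.** REML fit of the planned model (random site intercept, fixed period and group) with a Wald test at 1.96. Each scenario had 600 to 1,500 runs. Where repeated simulations differ, the range is given.

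| Site-by-period SD (points) | 6 sites: hand | 6 sites: simulated | 12 sites: hand | 12 sites: simulated |
|---|---|---|---|---|
| 0 | 5% | about 7% | 5% | 5–6% |
| 1 | 5.7% | 6.7% | 5.2% | 5.8% |
| 1.5 | 6.6% | 8.3% | 5.6% | 6.3% |
| 2 | 7.9% | 9.5% | 6.0% | 7.1% |
| 3 | 11% | 12–14% | 7.3% | 7–9% |
| 5 | 21% | 21–22% | 11% | 10% |

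With 6 sites and τ = 5, the empirical standard error was 4.46 points and the mean reported one 2.84. The ratio is 1.57, in line with √D = 1.55.

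An intervention effect that varies by site acts in the same direction. With a site-by-intervention SD of 5 points and no site-by-period shift, the planned model rejected in 11–15% of runs with 6 sites and 8–11% with 12.

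**Step 3: does the remedy work?** In the 6-site layout, adding a random site-by-period effect with a t reference brought rejection to 4–7%. With 12 sites and site-by-intervention variation, the rate stayed at 8% after that term was added.

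A second set of assumptions used 300 patients, 6 sites, 5 periods, individual SD 18 and site SD 4. Coverage of the nominal 95% interval was:
- no shifts: 95% with the planned model
- site-by-period SD 4: 88% planned, 95% with the added term (mean interval width 13.7 to 17.0 points)
- site-by-period SD 6: 86% planned, 96% with the added term (14.1 to 19.5 points)
- a further site-by-intervention effect, tested on 5 degrees of freedom: 99%, which is conservative

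**The case against.** The strongest reply is that this is a disclosed modelling choice. The SAP uses a model proposed for stepped wedge designs and states its assumption openly, and the document does not contradict itself. That stands. The weakness is that an assumption bearing on a co-primary endpoint is neither relaxed nor checked.

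The size of the effect is also open to challenge, and this largely stands. The 22% figure sets a site-by-period variance of 25 beside a site variance of 9, and nothing in the SAP supports that ratio. At an SD of 1 to 2 points, or with 12 sites, the excess is small. Part of it comes from the 1.96 reference, which the SAP does not specify: with 6 sites and no shifts, rejection is already about 7%. With a t reference on 14 degrees of freedom, SDs of 1, 1.5 and 2 give about 4%, 6% and 6%.

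A reader might infer from the SAP that such shifts are expected. The documents do not support that:
- Under Implementation, the SAP plans to report the "percent who received the decision aids from clinical personnel, percent who viewed the video in a clinical setting". These are percentages of patients from a per-patient checklist. They name neither site nor period, so they do not show a shift shared within a site and period.
- The mention of local education standards under Knowledge describes one source of items for the test. It does not say that sites teach differently.
- The SAP says nothing about educators changing.
- The assumption sentence concerns time trends. That the intervention effect is common to all sites follows from the list of model terms.

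A random effect also has limits as a remedy. It makes the interval honest about site-specific shifts, but it does not stop one programme's change in teaching from moving the estimate.

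**Conclusion.** The point holds in conditional form. The planned model fixes one random effect for site and a common period trend, and nothing in the SAP tests or relaxes this. If site-by-period variation in knowledge gain exists, the standard error for the knowledge co-primary would be too small. If it does not, the model is close to nominal. The direction follows from the model's structure and appeared in every simulation.

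The size cannot be computed from the SAP. Under the stated assumptions, type I error is about 7% to 22% for 6 sites and about 6% to 10% for 12 sites as the site-by-period SD goes from 1 to 5 points. The stronger claim, that the interval is too narrow as the plan stands, is not supported, because the SAP gives no evidence that such shifts occur. The change is worth making because it is cheap and offers protection where the assumption fails.

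**What to change.** - Add a random site-by-period effect to the model for the baseline 1 to baseline 2 change, with a small-sample correction such as Kenward-Roger. Use the same structure for the continuous secondary scales.
- Prespecify a sensitivity analysis with a random site-by-intervention effect, and note that it can be conservative with few sites.
- Report a table of knowledge change by site and period.
- Revise the assumption sentence to say that the average trend over time is common to all sites and that sites may deviate from it randomly by period. Keep it in the SAP, since deleting it would remove a useful disclosure and the average trend is still assumed common.

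The cost is SAP wording and one more variance term in a model already planned. The interval widens when sites differ. With few sites the new variance may be estimated at zero, and the fit then returns to the planned model.

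### Adjustment covariates for the knowledge co-primary model are chosen by observed group imbalance, with no list, criterion or functional form fixed in advance

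*SAP*

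**What the plan says.** The Knowledge part of the SAP's Effectiveness section sets out a linear mixed model for repeated measures within patient. The model "included a random effect for site and fixed effect indicators of intervention group and stepped wedge time period". The question it must answer is whether the "change in knowledge score (percent correct) between baseline 1 and baseline 2 was different between the control and intervention groups".

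The covariate rule has two steps. First, "We will assess any differences in baseline covariate distribution by intervention group". Then the analysts "will include covariates that are imbalanced by group in this linear mixed model". The SAP gives no candidate list, no measure of imbalance and no cut-off. It does not say whether a selected covariate enters as a main effect or interacts with visit.

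The only baseline comparison method in the document is in the opening paragraph. There, characteristics "between those enrolled during the control period and those enrolled during the intervention period, will be compared using chi-square tests and t-tests". The Knowledge paragraph does not refer back to it.

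Under secondary outcomes, the same model is reused: "Differences in the continuous outcome scales by intervention group will be assessed via the linear mixed model described previously".

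**The concern.** A covariate is worth adjusting for when it predicts the outcome. Here the outcome is the change in knowledge between two surveys. The SAP selects on a different property, the observed difference between control and intervention patients. A strong predictor that looks balanced stays out, and a weak one that looks imbalanced goes in. The model for a co-primary endpoint is then settled only after group differences have been seen, and two analysts could reasonably reach different models from the same data.

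The design adds a complication. In a stepped wedge, group is tied to site and calendar period, so imbalance may be systematic as well as accidental. Chi-square and t-tests on individual patients take account of neither site nor period. If they drive the selection, they will flag covariates too often merely because sites differ in case mix.

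Finally, the estimand is a within-patient change. A covariate affects that contrast only if it enters in a form that acts on the change, and the SAP leaves the form open. If the secondary scales inherit the covariate rule along with the model, they inherit the same problem.

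**Working it through.** The SAP states no sample size, number of sites, threshold or covariate count, so there is no figure of its own to reproduce. Step 1 is algebra and needs only complete data. Steps 2 and 3 rest on assumed inputs.

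**1. What the form does to the contrast.** Let j = 0 at baseline 1 and j = 1 at baseline 2, G the group and X a baseline covariate. With X as a main effect:

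Y(i,j) = a + b·j + g·G(i) + d·G(i)·j + c·X(i) + site and period terms + u(i) + e(i,j)

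Subtracting the two surveys gives

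Y(i,1) − Y(i,0) = b + d·G(i) + [e(i,1) − e(i,0)]

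The term c·X(i) has gone, so d is not adjusted for X. Adding f·X(i)·j leaves f·X(i) in the change, and d is then adjusted.

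This was checked on one constructed dataset: 252 patients, complete data, a covariate shifted by 0.4 SD between groups, a patient random intercept and period main effects.

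| Model terms | Group term read | Estimate | SE |
|---|---|---|---|
| group × visit, no covariate | group × visit | 0.4519 | 0.1822 |
| plus covariate main effect | group × visit | 0.4519 | 0.1822 |
| plus covariate × visit | group × visit | 0.3791 | 0.1872 |
| group main effect only, no covariate | group | 0.7804 | 0.2279 |
| group main effect only, plus covariate | group | 0.5065 | 0.2065 |

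The data were built so that the covariate affects level, not change. The move in the third row therefore shows the mechanism and does not estimate bias in this trial.

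**2. Precision when the covariate acts on the change.** Assumptions:
- 6 sites, 7 periods and 6 patients per site and period, so 6 × 7 × 6 = 252 patients, with one site crossing at each step
- change scores with SD 1, period effects in the model and no site effect
- a covariate without systematic imbalance, entering if t-test p<0.05
- 2000 replicates

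| Correlation r with change | SD, never adjusted | SD, imbalance rule | SD, always adjusted | Rule ÷ always |
|---|---|---|---|---|
| 0 | 0.1699 | 0.1700 | 0.1704 | 0.998 |
| 0.3 | 0.1688 | 0.1684 | 0.1604 | 1.050 |
| 0.5 | 0.1717 | 0.1671 | 0.1487 | 1.124 |

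- Share of the available gain given up by the rule: at r = 0.3, (0.1684 − 0.1604)/(0.1688 − 0.1604) = 0.0080/0.0084 = 95%. At r = 0.5, (0.1671 − 0.1487)/(0.1717 − 0.1487) = 0.0184/0.0230 = 80%.
- Cross-check of never against always adjusting, by 1/√(1 − r²): 1.048 at r = 0.3 and 1.155 at r = 0.5. The simulation gives 0.1688/0.1604 = 1.052 and 0.1717/0.1487 = 1.155.
- Type I error lay between 0.044 and 0.056 over all three approaches. The Monte Carlo standard error is √(0.05 × 0.95/2000) = 0.005, so this is consistent with 5%.

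**3. How often a covariate with no systematic imbalance is flagged.** Without clustering, the chance that at least one of k independent covariates is flagged at 0.05 is 1 − 0.95^k: 23%, 40%, 54% and 64% for k = 5, 10, 15 and 20.

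With unclustered t-tests in layouts of 4, 6 and 10 sites (120, 252 and 330 patients; 4000 replicates), flag rates at a nominal 5% were:

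| Assumed covariate ICC | 0.02 | 0.05 | 0.10 | 0.20 |
|---|---|---|---|---|
| Flagged | about 7% | 8–10% | 11–15% | 17–24% |

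At a trigger of 0.20 with ICC 0.20, the rate was 38–45%. Over the triggers (0.05 to 0.20) and ICCs (0 to 0.20) tried, such a covariate was left out about 55% to 95% of the time.

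**The case against.** Several objections stand and limit the point.

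- **The tests are not stated to be the selection rule.** A reader might infer that the SAP selects covariates by chi-square and t-test p-values that ignore site. The opening paragraph says only that baseline characteristics "will be compared using chi-square tests and t-tests", and that sentence also covers enrolled against screened-only participants. The Knowledge paragraph names no test or cut-off. The link is a reasonable inference, no more, and the flag rates in step 3 apply only if it is right.
- **The two harms need different models.** If covariates cancel from the contrast, their choice cannot move the estimate or cost precision. If their choice matters, they do not cancel. The two cannot be charged together. Because the SAP does not fix the form, each has to be stated conditionally.
- **Failure of the adjustment is not established.** A reader might conclude that the rule can never remove confounding. That needs main effects only, a group-by-visit contrast and complete data. The SAP writes out none of the first two and expects missing data, to be handled under missing at random.
- **Imbalance may be real.** With group tied to site and period, there is a rationale for adjusting for systematic differences. Site, period and the patient's own baseline 1 score are already in the model. Over-flagging under clustering would also make omission less frequent.
- **No validity failure was shown.** Type I error held in the simulations, although these covered only a covariate without systematic imbalance.

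None of this supplies a covariate list, a criterion or a form, or a reason to prefer observed imbalance to prognostic value as the basis for the primary model. Nor is the matter simply left to the protocol: the SAP states a selection rule, and that rule is the weak point.

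**Conclusion.** The point holds in conditional form. The covariate set for a co-primary model is chosen from observed group differences, and its criterion and functional form are left open.

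- **If covariates act on the change**, the estimate depends on which covariates were flagged, and the rule gives up most of the precision that pre-specification would bring. The SD of the contrast is about 5% larger at r = 0.3 and 12% larger at r = 0.5. This rests on the assumed layout, a p<0.05 trigger and a covariate without systematic imbalance.
- **If covariates enter only as main effects beside a group-by-visit contrast**, then with complete data the adjustment leaves estimate and standard error as they were, and cannot remove confounding of the change.

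A reader might go further and say that prognostic covariates will mostly be left out, or that false positives will rise. The first depends on a threshold and clustering that the SAP does not give, and on imbalance being accidental. The second is not supported by the simulations. The matter should be corrected, but it concerns precision, pre-specification and whether the adjustment does its job; it is not a demonstrated bias in the trial's result.

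**What to change.** Replace the imbalance rule in the Knowledge paragraph with the following:

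1. Name, before the analysis, a short list of baseline covariates already collected and expected to predict change in knowledge.
2. Include all of them in the primary model whatever their observed balance.
3. State the form so that they act on the change: a covariate-by-visit term for each, or an equivalent model with the change as outcome. Write out the group-by-visit term that carries the co-primary contrast.
4. Report baseline balance between control and intervention periods descriptively, and do not use it to select the primary model.
5. Because imbalance may be systematic in this design, keep adjustment for any further imbalanced covariates as a labelled sensitivity analysis.
6. State whether the same covariate list applies to the continuous secondary scales.

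The cost is SAP wording and a few degrees of freedom, with no new data. Including a covariate that turns out not to predict change costs little: in the simulation at r = 0, the SD of the contrast was 0.1704 with it and 0.1699 without it, a difference of 0.3%.
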